6.0 STUDY CONDUCT

6.1 **Duration of Therapy**

Therapy in LCCC1524-ATL involves just one infusion of ATLCAR.CD30 cells. Treatment with one infusion will be administered unless:

- Subject decides to withdraw from study treatment, OR
- General or specific changes in the subject's condition render the subject unacceptable for further treatment in the judgment of the investigator.

6.2 **Duration of Follow-Up**

Subjects will be followed for up to 15 years or until death, whichever occurs first. Subjects removed from study for unacceptable adverse events will be followed until resolution or stabilization of the adverse event.

Subjects who experience disease progression and start alternate therapy after receiving a cell infusion(s) will still be required to complete abbreviated follow up procedures outlined in APPENDIX IV - Abbreviated Follow Up Required After Initiating Alternative Therapy (section 18.4).

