6.4 Study Withdrawal

If a subject decides to withdraw from the study (and not just from protocol therapy) an effort should be made to complete and report study assessments as thoroughly as possible. At the time of withdrawal, the investigator should attempt to establish as completely as possible the reason for the study withdrawal.

- The subject should be asked if they are willing to allow for the abstraction of relevant information from their medical record in order to meet the long term follow up (e.g., survival) objectives outlined in the protocol.
- A complete final evaluation at the time of the subject's study withdrawal should be obtained with an explanation of why the subject is withdrawing from the study.
- If the subject is noncompliant and does not return for an end of study follow up assessment, this should be documented in the eCRF.
- If the reason for removal of a subject from the study is an adverse event, the principal specific event will be recorded on the eCRF.

Excessive subject withdrawals from protocol therapy or from the study can render the study un-interpretable; therefore, unnecessary withdrawal of subjects should be avoided.

$7.0\ {\rm DESCRIPTION}\ {\rm OF}\ {\rm STUDY}\ {\rm PROCEDURES}$

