CD30 is also expressed on first trimester decidua so there may be a risk of miscarriage in females of child-bearing potential if the cells persist long term. To evaluate this risk we will add a question about miscarriage to our annual follow up evaluation in these patients and report any such events in our annual IND report.

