10.3.2 Pregnancy

Pregnancies and suspected pregnancies (including a positive pregnancy test regardless of age or disease state) of a female subject at UNC or at a multicenter site, occurring while the subject is on study, or within 30 days of the subject's last dose of study product should be recorded as SAEs. The subject is to be discontinued immediately from the study.

For multicenter sites, the pregnancy, suspected pregnancy, or positive pregnancy test must be reported to the Multicenter Project Manager immediately via email ([contact]) or facsimile to [contact]. The female subject should be referred to an obstetrician-gynecologist, preferably one experienced in reproductive toxicity for further evaluation and counseling.

The Investigator will follow the female subject until completion of the pregnancy and must document the outcome of the pregnancy (either normal or abnormal outcome) and report the condition of the fetus or newborn to the Multicenter Project Manager. If the outcome of the pregnancy was abnormal (e.g., spontaneous or therapeutic abortion),

the Investigator should report the abnormal outcome as an AE. If the abnormal outcome meets any of the serious criteria, it must be reported as an SAE.

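### The pregnancy rule in section 10.3.2 ends observation after the single infusion, against the 15-year follow-up, and section 6.2 is unclear on follow-up after removal for an adverse event

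*Combined protocol and SAP*

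**What the plan says.** - **Treatment (6.1).** "Therapy in LCCC1524-ATL involves just one infusion of ATLCAR.CD30 cells".
- **Length of follow-up (6.2).** "Subjects will be followed for up to 15 years or until death, whichever occurs first". Footnote 1 of the Time and Events Table (4.2) and section 7.4 give the same 15 years.
- **Adverse events (6.2, next sentence).** "Subjects removed from study for unacceptable adverse events will be followed until resolution or stabilization of the adverse event". Nothing is said about what follows.
- **Progression (6.2 and Appendix IV).** Subjects who progress and start other therapy stay in an abbreviated schedule of history, performance status, correlative samples and survival, yearly to 15 years or death.
- **Withdrawal (6.4).** This section separates leaving the study from leaving protocol therapy. It foresees removal for toxicity: "If the reason for removal of a subject from the study is an adverse event, the principal specific event" is to be entered on the eCRF. It also asks for permission to abstract records for long-term objectives such as survival, but in a section about subjects who decide to withdraw.
- **Pregnancy (10.3.2).** The rule covers a pregnancy "occurring while the subject is on study, or within 30 days of the subject's last dose of study product", to be recorded as an SAE. It continues: "The subject is to be discontinued immediately from the study". It then adds: "The Investigator will follow the female subject until completion of the pregnancy and must document the outcome of the pregnancy". Spontaneous abortion is named as an abnormal outcome to be reported as an AE.
- **Miscarriage risk (8.3, cross-reactivity).** Because CD30 is found on first-trimester decidua and the cells may persist, "we will add a question about miscarriage to our annual follow up evaluation in these patients".
- **Analysis (11.3).** PFS is estimated by Kaplan-Meier, with no censoring rule (11.3.4). No analysis of OS is described.

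**The concern.** In a repeated-dosing trial, discontinuing a pregnant subject protects her from further exposure. Here the only exposure is over once the cells are infused, so leaving the study takes away observation and nothing else. For a gene-modified product that observation is the purpose of the 15-year plan: persistence, new malignancy, delayed events and survival. The protocol itself names a reproductive risk that depends on long-term persistence, then ends annual follow-up for the women who conceive.

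The adverse-event sentence raises a related question. If a subject removed for toxicity is followed only until the event settles, the trial loses late outcomes in someone whose toxicity may be related to prognosis. With 12 to 18 subjects, one such loss is visible in a survival curve.

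**Working it through.** The plan gives no figure to reproduce: OS and PFS have no sample-size or event calculation. The check is mainly a comparison of passages, with a short calculation for scale.

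**1. What discontinuation does after infusion.** Section 6.1 gives one infusion, and the removal criteria in 6.1 and 6.3 concern giving it. After it, no protocol therapy remains to stop. Section 6.4 distinguishes therapy from study, and 10.3.2 uses the word study. Followed literally, the rule ends follow-up.

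**2. What is kept and what is lost after a pregnancy.**

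| Item | After discontinuation under 10.3.2 |
|---|---|
| Outcome of the index pregnancy, including miscarriage | Kept (10.3.2) |
| Later pregnancies, by the annual question (8.3) | No provision |
| Transgene persistence (4.2 footnote 11a, 7.4) | No provision |
| New malignancies and delayed events (4.2 footnote 17, 7.4) | No provision |
| Survival | No provision, unless 6.4 abstraction is extended to her and she agrees |

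**3. What 6.2 does for adverse events.** The sentence sets how long already removed subjects are followed. No section says when an adverse event requires removal. Progressors have a written fallback in Appendix IV; subjects removed for an adverse event have none.

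**4. Size per removed subject.** Section 11.2 gives 12 to 18 subjects. The share is 1/n: 1/18 = 5.6% and 1/12 = 8.3%.

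**5. Illustration for a survival estimate.** Assume k subjects are removed at about week 6, before any event, and that the Kaplan-Meier estimate at 24 months among the n − k retained is S = 0.70 (an assumption; the documents give no such value). If all removed subjects later fail, the true proportion is S(n − k)/n. If none fail, it is [S(n − k) + k]/n. The width is k/n.

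- n = 18, k = 1: 0.70 × 17 = 11.9; 11.9/18 = 0.66 and 12.9/18 = 0.72.
- n = 18, k = 2: 0.70 × 16 = 11.2; 11.2/18 = 0.62 and 13.2/18 = 0.73.
- n = 12, k = 1: 0.70 × 11 = 7.7; 7.7/12 = 0.64 and 8.7/12 = 0.73 (0.725).
- n = 12, k = 2: 0.70 × 10 = 7.0; 7.0/12 = 0.58 and 9.0/12 = 0.75.

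If removed subjects stay in follow-up, these bounds close.

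**The case against.** **The adverse-event sentence removes nobody.** This stands. It can be read as a minimum for the event, with the 15 years continuing, and 6.4 discourages unnecessary withdrawal. A reader might infer that the protocol orders subjects with severe toxicity out of the study. It does not. What remains is an ambiguity.

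**Toxicity brings more surveillance, not less.** Footnote 17 of 4.2 and section 7.4 allow more frequent observation after a related delayed event, and 7.5.2 triggers RCR testing. This also stands. A reader might infer that the worst-affected subjects lose gene-therapy surveillance by design; these sections point the other way. They do not say what happens to a subject already removed.

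**Miscarriage is captured.** For the index pregnancy this is right. It would be wrong to infer that women who conceive drop out of the miscarriage assessment. The loss is what comes later.

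**On study may mean less than 15 years.** The separate 30-day clause would be nearly redundant after one infusion if the period ran 15 years, and the term is not defined. Even on a narrow reading, a pregnancy within 30 days of infusion would end almost all of the 15-year follow-up.

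**Pregnancies may be few.** Sections 5.1 and 5.2 ask women of childbearing potential to be willing to use contraception or abstain during the study and for six months after, and 1.5.3 lists infertility among late complications. This stands against any estimate of numbers. The sex split in 1.5.3 describes all new Hodgkin cases, not this transplant population, and no conception rate is given.

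**Informative censoring is not written anywhere.** Correct: it is an inference. It is plausible for removal because of toxicity. For pregnancy the direction is unknown, and selection could favour healthier women. Scheduled imaging ends at 24 months, so later pregnancies matter little for PFS.

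**Conclusion.** The conflict in 10.3.2 is real. Taken as written, the pregnancy rule ends observation after a single infusion, against the 15-year follow-up in 4.2, 6.2 and 7.4 and the annual question in 8.3. The index pregnancy is covered; later pregnancies, persistence, late effects and survival are not.

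Section 6.2 is ambiguous, not a second mandatory rule. On its plain reading, a subject removed for an adverse event has no continued survival or late-effects follow-up of the kind that Appendix IV gives progressors. Such removals could be informative for OS and PFS, and 11.3 has no rule to handle them.

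Each removal is 5.6% of 18 or 8.3% of 12 subjects. How many will occur cannot be estimated from the documents, and the survival bounds above rest on an assumed 24-month value and removal at week 6. OS and PFS are secondary endpoints; the six-week DLT assessment and the MTD are little affected. The point deserves correction but does not threaten the primary objective.

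**What to change.** Reconcile 6.2, 6.4, 8.3 and 10.3.2 as follows.

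- State in 6.2 and 10.3.2 that, after infusion, neither a pregnancy nor an adverse event ends scheduled follow-up for survival, disease status and delayed events unless the subject withdraws consent.
- State in 6.2 that following an adverse event until it resolves or stabilizes is a minimum for that event and does not replace the 15-year schedule.
- Align 6.4 with this, and make clear that the annual question in 8.3 continues after a pregnancy.
- Leave SAE reporting of pregnancy and follow-up to its outcome unchanged.
- A one-line censoring rule in 11.3.4, with a matching line for OS, would settle how any remaining early exits are treated.

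The cost is a few sentences and an amendment through the IRB, possibly with a revised consent form (section 14.0). The visits are already on the schedule for infused subjects. No dose, eligibility rule or sample size changes.

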6.3 Removal of Subjects from Protocol Therapy

Subjects will be removed from protocol therapy and the PI notified when any of the criteria listed in section 6.1 apply. The reason for discontinuation of protocol therapy will be documented on the eCRF.

In case a subject decides to prematurely discontinue protocol therapy ("refuses

treatment"), the subject should be asked if she or he may still be contacted for further scheduled study assessments. The outcome of that discussion should be documented in both the medical records and in the eCRF.

6.4 Study Withdrawal

If a subject decides to withdraw from the study (and not just from protocol therapy) an effort should be made to complete and report study assessments as thoroughly as possible. At the time of withdrawal, the investigator should attempt to establish as completely as possible the reason for the study withdrawal.

- The subject should be asked if they are willing to allow for the abstraction of relevant information from their medical record in order to meet the long term follow up (e.g., survival) objectives outlined in the protocol.
- A complete final evaluation at the time of the subject's study withdrawal should be obtained with an explanation of why the subject is withdrawing from the study.
- If the subject is noncompliant and does not return for an end of study follow up assessment, this should be documented in the eCRF.
- If the reason for removal of a subject from the study is an adverse event, the principal specific event will be recorded on the eCRF.

Excessive subject withdrawals from protocol therapy or from the study can render the study un-interpretable; therefore, unnecessary withdrawal of subjects should be avoided.

$7.0\ {\rm DESCRIPTION}\ {\rm OF}\ {\rm STUDY}\ {\rm PROCEDURES}$

7.1 Clinical Assessments

Clinical assessments will be performed as outlined in the Time & Events Table.

7.1.1 Disease Assessment Guidelines for Cutaneous Lymphomas

Lymphomatoid papulosis (LP) or primary cutaneous anaplastic large cell lymphomas (ALCL):

This is by definition a skin only disease.

- 1. Bone marrow biopsy is not required
- 2. Imaging will be done:
 - **Pre-transplant** (not required at procurement) to assess that there isn't unexpected nodal or visceral disease. Imaging should be performed within 60 days prior to transplant.
 - If scans show any enlarged lymph nodes >1.5cm at baseline then that subject will be treated as systemic lymphoma and followed as outlined in the Time & Events Table in section 4.2 for other lymphomas
 - If the baseline scans performed prior to transplant are negative there will be no further imaging and response will be based on assessment of skin disease on physical exam performed as outlined in the Time & Events Table in section 4.2.
- 3. Dermatology consult:
 - Subjects will need to see a dermatologist within 30 days prior to transplant.
 - They will need to see a dermatologist at the week 6 visit.
 - Thereafter they can be followed by the oncologist or dermatologist.

Page 68 of 154

Study Assessments	Sc	reening	ATLCAR Treatment	Follow-Up						
LP or ALCL	Pre- procure- ment	Pre- Transplant	W0D1	W1D1	W2D1	W3D1	W4D1	W6D1		
Dermatology consult		Х						Х		
Tumor imaging		X*		*if LN >1.5cm at baseline then perform scans per the Time & Events Table *If scans negative at baseline then response based on physical exam the Time & Events Table						

Table 5Study Assessments for LP and ALCL

Mycosis fungoides or Sézary syndrome:

- 1. Bone marrow biopsy is not required
- 2. Imaging will be done:
 - *Pre-transplant* (not required at procurement). Imaging should be performed within 60 days prior to transplant.
 - If scans show any enlarged lymph nodes >1.5cm at baseline then that patient will have repeat scans performed at the 6 week assessment. Thereafter scans will only be performed if there is a partial response or better in the skin disease on physical exam performed as outlined in the Time & Events Table
 - If the baseline scans performed prior to transplant are negative there will be no further imaging and response will be based on assessment of skin disease on physical exam performed as outlined in the Time & Events Table.
- 3. Peripheral blood will be sent for flow cytometry/ leukemia profile.
 - Pre-transplant (within 30 days prior to transplant):
 - If this assessment shows no disease involvement in blood then it does not need to be repeated
 - If this assessment shows disease involvement in blood then it should be repeated
 - at 6 weeks post cell infusion
 - at 3 months post cell infusion

- Thereafter this assessment should be repeated only to confirm complete remission (CR) based on skin exam
- 4. Dermatology consult:
 - Subjects will need to see a dermatologist within 30 days prior to transplant.
 - They will need to see a dermatologist at the week 6 visit after the cell infusion.
 - Thereafter they can be followed by the oncologist or dermatologist.

Table 6Study Assessment s for Mycosis Fungoides and Sézary Syndrome

Study Assessments	Sc	reening	ATLCAR Treatment								
Mycosis fungoides and Sézary syndrome	Pre- procure- ment	Pre- Transplant	W0D1	W1D1	W2D1	W3D1	W4D1	W6D1	M3D1		
Blood for flow cytometry/		Х						Х	Х		
leukemia profile											
Dermatology consult		Х						Х			
Tumor imaging		Х		If scans show any enlarged LN >1.5cm at baseline, then repeat scans performed at the 6 week assessment. Thereafter scan if PR or better in skin disease If baseline scan negative: repeat imaging only if PR or better in skin disease post cell infusion							

7.2 Screening and Treatment Assessments

7.2.1 Pre-procurement

Check eligibility

Clinical evaluation: complete history, Karnofsky or Lansky performance status

Laboratory studies:

• **Pregnancy Test:** serum pregnancy testing will be done in female subjects of childbearing potential (within 72 hours prior to procurement)

- Pulmonary function tests: Including FEV1, FVC and DLCO
- Ejection Fraction
- HIV, HBV, HCV testing required (see footnote #6 of Time & Events Table)
- Only labs listed below are required (within 7 days of procurement) NOTE: if the following lab tests have already been performed within 7 days of procurement as part of SOC pre-transplant work-up (i.e., as part of hematology labs or CMP collected which includes BUN, creatinine, Na, K, Cl, CO2, glucose, calcium, albumin, total protein, total bilirubin, ALT, AST, alkaline phosphatase), they do not need to be repeated:
 - o Hg
 - o AST
 - o Bilirubin
 - Serum creatinine

Imaging: To assess disease status, imaging will be performed at baseline (within 60 days prior to ASCT). The choice of imaging will depend on what studies have been most informative in following the subject's disease (i.e., PET, CT scans, MRI, nuclear imaging). If subject has cutaneous lymphoma see section 7.1.1 for details.

Patient reported outcome questionnaires for adult subjects (optional): PROMIS Global Health Scale, PROMIS Physical Function, and selected questions from NCI PRO-CTCAE. Administered at time of screening consent.

Procurement: See section 4.1.1; to take place prior to ASCT. Procurement may occur prior to or after PBSC mobilization. If procurement occurs after PBSC mobilization, it must occur at least 7 days after ending use of G-CSF.

7.2.2 Pre-infusion

Check eligibility

Clinical evaluation: History, physical examination, Karnofsky or Lansky performance status

Laboratory studies:

- Pregnancy Test: serum pregnancy testing will be done in female subjects of childbearing potential (within 72 hours prior to infusion)
- Pulse Oximetry
- CBC with differential and platelets: (required within 24 hours prior to infusion)
- CMP: (required within 24 hours prior to infusion) BUN, creatinine, Na, K, Cl, CO2, glucose, calcium, albumin, total protein, total bilirubin, ALT, AST, alkaline phosphatase
- Thyroid function: obtained pre-infusion
- Dermatology consult needed for cutaneous lymphomas only
- Blood taken for leukemia profile and flow cytometry (mycosis fungiodes and Sezary syndrome patients only)
- Blood Sample for Correlative Studies (see section 7.5)
 - Function and persistence studies: Including in vitro reactivation of PBMCs in subjects for whom the appropriate reagents are available and immunophenotyping
 - Replication competent retrovirus (RCR): Sample collected preinfusion for PCR testing
 - Quantitative PCR
 - HAMA testing
 - Cytokine testing: obtained pre and post infusion

Toxicity: Toxicity will be assessed according to the NCI CTCAE v. 4.0.

CoA: Generated at completion of required studies for production/QA of cell (available prior to planned infusion)

Patient reported outcome questionnaires for adult subjects (optional): PROMIS Global Health Scale, PROMIS Physical Function, and selected questions from NCI PRO-CTCAE. This will be collected on the day of infusion prior to infusion.

7.2.3 Treatment (D1 Week 0)

ATLCAR.CD30 cells infused after evidence of hematologic recovery post ASCT, see section 4.1.2 for definition of recovery. This will generally occur between 14 and 20 days following infusion of autologous stem cells following high-dose chemotherapy. All subjects will receive their ATLCAR.CD30 infusion at the lead site, the University of North Carolina, Chapel Hill.

Laboratory studies:

- Blood Sample for Correlative Studies (see section 7.5 and LCCC1524-ATL Study Laboratory Manual)
 - Function and persistence studies: 3-4 hours post infusion
 - Quantitative PCR: 3-4 hours post infusion Genetic analysis (see Section 7.5.5)

Toxicity: Toxicity will be assessed according to the NCI CTCAE v. 4.0, CRS Toxicity Grading Scale (See APPENDIX VIII- CRS Toxicity Grading Scale and Management Guidelines).

7.3 Short-term Follow-up

7.3.1 D1 Week 1

Clinical evaluation: History, physical examination

Laboratory studies:

- CBC with differential and platelets
- CMP: BUN, creatinine, Na, K, Cl, CO2, glucose, calcium, albumin, total protein, total bilirubin, ALT, AST, alkaline phosphatase
- Blood Sample for Correlative Studies (see section 7.5)
 - Function and persistence studies
 - Quantitative PCR
 - Cytokine testing
 - Genetic analysis (see Section 7.5.5)
Toxicity: Toxicity will be assessed according to the NCI CTCAE v. 4.0, CRS Toxicity Grading Scale (See APPENDIX VIII- CRS Toxicity Grading Scale and Management Guidelines).

Patient reported outcome questionnaires for adult subjects (optional): PROMIS Global Health Scale, PROMIS Physical Function, and selected questions from NCI PRO-CTCAE

7.3.2 D1 Week 2

Clinical evaluation: history, physical examination, Karnofsky or Lansky performance status.

Laboratory studies:

- CBC with differential and platelets
- CMP: BUN, creatinine, Na, K, Cl, CO2, glucose, calcium, albumin, total protein, total bilirubin, ALT, AST, alkaline phosphatase
- Blood Sample for Correlative Studies (see section 7.5)
 - Function and persistence studies
 - Quantitative PCR
 - Cytokine testing
 - Genetic analysis (see Section 7.5.5)

Toxicity: Toxicity will be assessed according to the NCI CTCAE v. 4.0, CRS Toxicity Grading Scale (See APPENDIX VIII- CRS Toxicity Grading Scale and Management Guidelines).

Patient reported outcome questionnaires for adult subjects (optional): PROMIS Global Health Scale, PROMIS Physical Function, and selected questions from NCI PRO-CTCAE

